5.8 Receiving, Storage, Dispensing and Return

5.8.1 Receipt of Drug Supplies

Nicotinic acid will be obtained in powder form and be compounded in the Research Pharmacy for intravenous administration, following Compounding Procedures and an approved compounding formula worksheet specific to each patient.

Upon receipt of the drug, an inventory will be performed and logged by research pharmacy technicians accepting the shipment.

5.8.2 Storage

Niacin storage: The investigational drug will be packaged in 10 mL amber vials and be refrigerated away from light in a temperature setting of 2-8°C. After compounding, a sterility date applied is 90 days with refrigerated storage. Niacin preparation is sterilized by a sterile filtration procedure using a sterile 0.2 micron filter.

Placebo storage: 0.9% NaCl will be stored at USP controlled temperature.

Storage location: Study drug and placebo will be stored at SMH Research Pharmacy that is secure and can be only accessed by research pharmacy personnel.

Light conditions: Amber glass vials provide light protection.

Container closure components: 10 mL amber Type 1 glass vials Wheaten item # 223761 are used for the container. The vials are depyrogenated through a washing cycle and are sterilized through a steam sterilization cycle.

The stoppers are West Pharmaceutical Flurotec 20 mm stoppers item #19700021. We purchase them as 'ready to sterilize' and subsequently sterilize them through repackaging and a steam sterilization cycle.

Sterility and bacterial endotoxins test methods: Sterility testing is accomplished through membrane filtration, using Millipore Steritest canisters. In a sterile environment, the contents of an appropriate number of vials (based on USP 71) are filtered through the canister set and are flushed with 0.9% sodium chloride for injection, USP. The canisters are incubated at appropriate temperatures for the media for 14 days.

Endotoxin testing is completed by an outside laboratory (ARL Bio Pharma). Limits are calculating according to USP 85 or if present, the USP monograph for the injection.

5.8.3 Dispensing of Study Drug

Regular study drug reconciliation will be performed to document drug assigned, drug dispensed, drug returns, and drug remaining. This reconciliation will be logged on the drug reconciliation form and reported by Research Pharmacy.

5.8.4 Return or Destruction of Study Drug

All medications would be given on site. Any patient specific unused medication will be destroyed on site.

6 Study Procedures

Table 1 below lists all of the assessments and indicates with an "x" the visits when they are performed. Subjects should be seen for all visits on the designated day and time.

Subjects who are discontinued before completing the study, and those who withdraw prematurely from the study for any reason, should be scheduled for a visit as soon as possible, at which all of the assessments listed for the "end of Study" visit will be performed. Study visits will occur at Screening, Visit 1 and Visit 2/End of Study.

The maximum duration of the clinical investigation is up to 8 weeks from enrollment (signing of consent, which allows for a 14 day screening period).

Schedule of Events			
	Screening	Inpatient Visit 1	Inpatient Visit 2
Study Day	-14	0	28-56
Written informed consent	X		
History and demographics	X		
Concurrent med reconciliation	X		
Height	X		
Weight	X	X	X
Vitals	X	X	X
Laboratory tests ^a	X*		
Single-slice abdominal CT	X		
DEXA scan	X*		
Adverse event evaluation	X	X	X
Pregnancy test	X ^b	X ^c	
Study Agent (niacin administration)		X	
Insulin and glucose administration		X	X
Isotope administration		X	X
Resting energy expenditure		X	X
Muscle Biopsies		X	X
Adipose biopsies		X	X

a: Complete metabolic panel, CBC w/differential, Lipid Panel, HbA1C, liver function tests if not part of complete metabolic panel

b: Serum pregnancy test (women of childbearing potential) at screening

c: Urine pregnancy test (women of childbearing potential) ≤ 48 hours prior to study drug administration.

*Research DEXA scan, labs, and CT scan completed in the previous 3 months may be used in place of repeating these.

6.1 Screening Visit

The data that will be collected on each subject at the screening visit are as follows:

- Confirmation of informed consent
- Vital signs (Blood pressure, pulse rate, respiratory rate, and body temperature)
- Body weight and height
- Confirmation of meeting all the Inclusion criteria and none of the exclusion criteria
- Demographics and medical history
- Pregnancy test – serum pregnancy test (for females of childbearing potential)
- Laboratory examinations: Complete Blood Count, Fasting lipid profile, Alkaline Phosphatase, Electrolyte Panel, AST, ALT, HbA1c (for diabetics), Fasting Glucose, Serum Creatinine. Overnight fasting is required and will be documented in the EMR by CRTU nursing staff.
- Body composition as measured by Dual-energy x-ray absorptiometry* (see section 4.3) and abdominal CT scan * (see section 4.3).

6.2 Visit 1 (In-patient visit, 1 night stay)

At visit 1 the subjects will undergo the following:

- Admission to in-patient facility the evening prior to scheduled biopsies
- Negative urine pregnancy test (for females of childbearing potential only) 48 hours prior to dosing.
- Vital signs (blood pressure, pulse rate, respiratory rate, and body temperature)
- Body weight
- Concomitant and non-drug therapies
- Niacin or saline infusion started the evening prior

Volunteers will be asked to stop taking any aspirin or ibuprofen from three days before to three days after their overnight stays.

All participants will consume an isoenergetic diet (weight stable, 45% carbohydrate, 20% protein and 35% fat) from the Mayo Clinical Research and Trials Unit (CRTU) for 1-3 days prior to the niacin infusion study and 3 days before the saline control study. This will assure consistency of energy intake and nutrient composition prior to the study saline control study that is helpful in reducing variability in plasma FFA concentrations.

Following admission to the CRU the evening prior to the studies a forearm intravenous catheter will be placed for infusion of niacin, insulin, glucose and isotopic tracers. T2DM volunteers taking insulin will be asked to withhold their long-acting insulin for 3 days prior to the study, manage their blood sugar with short acting insulin, and receive an overnight, monitored infusion of regular insulin to maintain blood glucose values between 4.5-5.5 mmol/L. At 2100 h the infusion of intravenous niacin (or saline) will begin. The initial niacin dose will be 0.6 mg/min and, depending upon symptoms, the rate increased by 0.4 mg/min increments to a goal of 1.4 mg/min. A retrograde intravenous catheter will be placed to allow for blood sampling at 2200 h, 2400 h, 0200 and 0400 h. The niacin/saline infusion will be continued until 0900 h the following morning. The niacin infusion will be weaned off gradually in order to prevent a rebound increase in plasma FFA. Depending upon the degree of overnight suppression of FFA concentrations, the dose may be adjusted downwards or upwards in subsequent studies to a maximum of 2.8 mg/min in subsequent studies. At 0400 h an infusion of $[U-^{13}C]palmitate$ (330 nmol/min) will be initiated to trace FFA contribution to intramyocellular lipids in the euinsulinemic state (13,15). At 0600 h an infusion of $[6-^2H_2]glucose$ will be started to trace glucose metabolism and continued till the

end of the study. Resting energy expenditure will be measured by indirect calorimetry to permit interpretation of FFA flux data. A series of blood samples will be collected between 0830 and 0900 h to measure steady state plasma palmitate and glucose enrichment and concentrations.

The volunteers will then undergo a vastus lateralis muscle biopsy for measurement fatty acid metabolites and to provide material for the “pre-clamp” measures of insulin signaling and the niacin infusion will be tapered to 25% of their overnight dose.

Insulin regulation of muscle glucose uptake and fatty acid metabolism will be assessed using a primed, constant infusion of insulin at a dose of 1.0 mU/kg/min. Arterialized venous blood samples will be collected from the same retrograde IV catheter using the hot box with a temperature of 131 degrees Fahrenheit, to allow measurement of hormone, tracers and substrate concentrations over the 30 min prior to the insulin clamp and the last 30 min of the insulin clamp. Blood glucose will be measured every 10 min throughout to allow the glucose infusion rate to be adjusted to maintain euglycemia. Resting energy expenditure will be measured by indirect calorimetry to permit interpretation of FFA flux data. (79).

Adipose tissue biopsies will be collected from the abdominal region under local anesthesia using sterile technique (82) at the same time as the first and last muscle biopsies. The adipose tissue samples (2-3 g from each site) will be immediately rinsed of blood and transported to our laboratory (~ 3 min walk from the CRTU).

There we will divide the specimen into smaller aliquots for collagenase digestion to be used for cell sizing (83), and immunohistochemistry.

The volunteers will be able to order a general meal after the biopsies. After this, the participants will be discharged from the CRTU.

6.3 Visit 2 (In-patient visit, 1 night stay)

After ~4 weeks subjects will return to the CRTU and the same procedure and guidelines as Visit 1 will be repeated with the saline/placebo.

7 Statistical Plan

7.1 Sample Size Determination

Power calculation:

Acipimox increased insulin-stimulated glucose disposal in undifferentiated obese subjects by ~10% ($P = 0.07$) and in T2DM by ~ 50%, whereas insulin-stimulated Akt phosphorylation increased by ~80% in both groups (66); IRS-1 tyrosine phosphorylation increased only in obese by 300%. In our hands, the reproducibility of insulin-stimulated glucose disposal is within ~5% with no intervention. If we obtain similar responses as Liang et al (66), we would have 90% power to detect a 10% improvement in insulin sensitivity in the obese group at a P of 0.05 with 5 subjects per group. However, because women may respond differently than men to changes in FFA (85), we propose to include more participants in order to allow sex-specific analysis. By selecting UBO volunteers we will likely have a more insulin resistant group than Liang (66), which should improve our statistical power to detect changes in lipid metabolites and insulin signaling. We can also expect some biological heterogeneity in the responses, which should be helpful in that we intend to understand the extent to which changes in insulin sensitivity relate to changes in intramyocellular DG and ceramides (86) and insulin signaling, for example by grouping participants post hoc to groups that have the greatest and least response to FFA suppression.

7.2 Statistical Methods

Descriptive Statistics

Baseline values for demographic, clinical, and outcome variables (primary and secondary) will be tabulated for the treatment groups. These analyses will help identify potential confounding variables to be used as covariates in sensitivity analyses. Distributions across subgroups used in randomization will be compared to assess whether the randomization was successful in equalizing distributions of these prognostic variables across treatment groups.

Our hypothesis will be tested by measuring the concentration of plasma palmitate (and total FFA) as well as the enrichment ($[U-^{13}C]$ and $[^2H_9]$ palmitate), and therefore flux of palmitate. We will measure the incorporation of $[U-^{13}C]$ and $[^2H_9]$ palmitate in DG and ceramides relative to plasma palmitate, as well as the insulin signaling assays and glucose disposal rates, specifically to test the effects of the lower FFA concentrations and lesser contribution of plasma FFA combined with improvements in insulin signaling and glucose disposal (ANCOVA). If glucose disposal and insulin signaling improvements in each group are accompanied by selective reductions in either ceramides or DG (especially the saturated species), this will suggest which of these is most likely responsible for the baseline impairments relative to the lean control state. It is possible that the UBO and T2DM will have different responses in ceramides and DG. For example, the portion of insulin resistance due to lipotoxicity in T2DM could be the combined effect of both DG and ceramides, whereas in UBO may be just one of these compounds. If the insulin signaling measures coincide with the changes in ceramides and DG in such a way as to confirm the pathways that have been described using cell/animal models are operative in humans, *in vivo*, this will provide an important confirmation that we can translate basic findings to human physiology. To the extent reduced lipolysis reduces FFA during the insulin clamp, we anticipate a lesser contribution of the $[9-2H]$ palmitate to DG and ceramides (repeated measures ANOVA).

A subtext to the DG and ceramide enrichment measures relative to plasma and palmitoyl-CoA is that, to the extent these molecules are synthesized from sources other than FFA, this will provide clues to alternate pathways that may be active in generating lipid signaling molecules. We will be able to understand whether excess ceramides are due to *de novo* synthesis as opposed to sphingomyelin hydrolysis and whether elevated DG is due to *de novo* synthesis or other sources, potentially including phospholipid hydrolysis. We believe that our ability to go beyond measures of concentrations by making more mechanistic assessments of the source of lipotoxicity is a strength of the proposed studies.

Handling of Missing Data:

The frequency and pattern of missing data will be evaluated to assess whether the data is missing completely at random, or whether a pattern exists that may suggest a systematic bias

with respect to the presence or absence of data. If the missing data appear to be missing completely at random, and if the amount of missing data is relatively small, the analysis will utilize all available data. Depending on the pattern and amount of missing data, multiple imputation methods may be considered, however given the proposed study has relatively modest sample size, the amount of missing data is anticipated to be small.

Primary Hypothesis:

In order to test Hypothesis 1 we will use the following pieces of data: a) subsarcolemmal (SS - largely equivalent to membrane associated DG (68)) DG concentrations, focusing primarily, but not solely, on 16:0/18:0, 16:0/16:0 and 18:0/18:0, as well as the enrichment in 16:0/18:0, 16:0/16:0 and 16:0/18:1 relative to plasma palmitate. This will provide us with as an index of de novo synthesis of DG from FFA; b) the baseline and insulin-stimulated changes in phosphorylation of Akt (66, 80); c) the increase in glucose disposal as a function of the increase in plasma insulin concentrations.

We will assess whether the SS DG concentrations and the incorporation of plasma FFA into DG (ratio of DG palmitate:plasma palmitate) differs between UBO and T2DM (ANOVA).

We will also test whether the concentrations or incorporation of plasma palmitate into the SS vs. IMF DG is related to changes in the proximal activation by phosphorylation of the insulin signaling pathway during the insulin clamp.

Secondary Hypotheses:

To address hypothesis 2 we will use a similar statistical approach, except using intramyocellular ceramide concentrations and enrichments relative to plasma palmitate in conjunction with Akt phosphorylation. Robust Akt phosphorylation in the face of high ceramide concentrations/synthesis from FFA would argue against the ceramide-PP2A mechanism of insulin resistance.

Interim Analysis

No interim analysis is proposed.

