7.3	SUBJECT POPULATION(S) FOR ANALYSIS	34
8	SAFETY AND ADVERSE EVENTS	34
8.1	DEFINITIONS	34
8.2	RECORDING OF ADVERSE EVENTS	38
8.3	REPORTING OF SERIOUS ADVERSE EVENTS AND UNANTICIPATED PROBLEMS	38
8.3.1	Sponsor-Investigator reporting: notifying the Mayo IRB	39
8.3.2	Sponsor-Investigator reporting: Notifying the FDA	41
8.4	UNMASKING/UNBLINDING PROCEDURES	42
8.5	STOPPING RULES	42
8.6	MEDICAL MONITORING	43
8.6.1	Internal Data and Safety Monitoring Board	44
9	DATA HANDLING AND RECORD KEEPING	45
9.1	CONFIDENTIALITY	45
9.2	SOURCE DOCUMENTS	45
9.3	CASE REPORT FORMS	45
9.4	RECORDS RETENTION	48
10	STUDY MONITORING, AUDITING, AND INSPECTING	49
10.1	STUDY MONITORING PLAN	49
10.2	AUDITING AND INSPECTING	58
11	ETHICAL CONSIDERATIONS	58
12	STUDY FINANCES	58
12.1	FUNDING SOURCE	58
12.2	CONFLICT OF INTEREST	59
12.3	SUBJECT STIPENDS OR PAYMENTS	59
13	PUBLICATION PLAN	59
14	REFERENCES	59

List of Abbreviations

LIST OF ABBREVIATIONS

AE	Adverse Event/Adverse Experience
CFR	Code of Federal Regulations
CRF	Case Report Form
DSMB	Data and Safety Monitoring Board
FDA	Food and Drug Administration
GCP	Good Clinical Practice
HIPAA	Health Insurance Portability and Accountability Act
IB	Investigator's Brochure
IND	Investigational New Drug Application
IRB	Institutional Review Board
PHI	Protected Health Information
PI	Principal Investigator
SAE	Serious Adverse Event/Serious Adverse Experience
SOP	Standard Operating Procedure

Study Summary

Title	Effects of Niacin on Intramyocellular Fatty Acid Trafficking in Subjects with Upper Body Obesity and Type 2 Diabetes Mellitus
Running Title	Effects of niacin on FFA in UBO and T2DM in insulin resistant states
Protocol Number	17-009977
Phase	Pilot Study
Methodology	Randomized, placebo-controlled; cross-over design
Overall Study Duration	2 years
Subject Participation Duration	6-8 weeks
Single or Multi-Site	Single site
Objectives	Evaluate the effect of niacin or placebo on intramyocellular fatty acid trafficking in subjects with upper body obesity and type 2 diabetes mellitus
Number of Subjects	10 upper body obese and 10 Type 2 diabetic participants will be recruited for this study for a total of 20 participants between the ages of 18-65 years.
Diagnosis and Main Inclusion Criteria	Individuals with upper body obesity and Type 2 diabetics will be included in the study.

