3.2 Number of Subjects

Ten upper body obese and 10 Type 2 diabetics (5 male and 5 female in each group) will be recruited to participate in this study to assure we have truly insulin resistant participants in whom improvements in insulin action can be expected.

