4.1 Inclusion Criteria

Subjects who meet the following criteria may be included in the study:

1. Males and females between 18 and 65 years of age who are able to comprehend instructions, follow study procedures, willing to sign an informed consent form, and consume an isoenergetic diet eating all meals from Mayo GCRC for at least 3 days prior to study.
2. **Overweight/Obese volunteers** will have a BMI $29.0 - 40.0 \text{ kg/m}^2$
 - **Upper body/visceral obesity (UBO)** in women will be those with a waist-hip ratio (WHR) > 0.85 and/or increased visceral fat by single slice CT scan and/or biochemical evidence of metabolic syndrome as determined by the investigators. Upper body obesity in men will be defined as a waist-hip ratio of > 0.95 and/or increased visceral fat by single slice CT scan and/or biochemical evidence of metabolic syndrome.
3. Volunteers with Type 2 Diabetes will have HbA1C between **6.5 and 11.5%**.
Hold metformin and sulfonylurea for 1 week prior study
Avoid pioglitazone due to long half life

4. Resting vital Signs are within the following range: 95 mmHg < systolic blood pressure < 160 mmHg
45 mmHg < diastolic blood pressure < 100 mmHg
40 bpm < heart rate < 100 bpm
5. Female subjects are eligible if they meet the following criteria:
 - Are not pregnant or nursing
 - All women of childbearing potential will have a negative serum pregnancy test at screening and a negative urine pregnancy test within 48 hours before administering study drug.
 - All women of childbearing potential will use an appropriate contraceptive method including barrier method, oral contraceptive medication, contraceptive device or abstinence while participating in the study.
6. Recent or Current research participation?

If Yes look at consent form and f/u visits:

- Medications that alter fat metabolism possibly given: if yes, exclude
- Weight possible changing in the study
- Amount of blood drawn during the study (if our study plus this one draw \geq 450 ml these should be separated by 8 weeks)

7. Previous labs:

- HbA1C < 6.5% for non-diabetic UBO
- Fasting glucose < 126 mg/dl for non-diabetic UBO
- Hb \geq 11.0 for women and \geq 12 for men
- platelets > 100 000

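### Section 7.2 would attribute impairment relative to lean people to DG or ceramide on the strength of a 'selective' fall, but the trial has no lean reference and specifies no direct DG-versus-ceramide comparison

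*Combined protocol and SAP*

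**What the plan says.** Section 7.2 (Statistical Methods) describes a pattern of results and what will be read from it. If glucose disposal and insulin signaling improve in a cohort and the improvement is "accompanied by selective reductions in either ceramides or DG (especially the saturated species", then "this will suggest which of these is most likely responsible for the baseline impairments relative to the lean control state". The sentence applies cohort by cohort.

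The cohorts are fixed in section 3.2: "Ten upper body obese and 10 Type 2 diabetics (5 male and 5 female in each group) will be recruited". The Study Summary gives the same total of 20. Section 4.1 sets a BMI of 29.0 to 40.0 kg/m² for the obese volunteers.

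The two lipids are handled in parallel. For DG, section 7.2 states: "We will assess whether the SS DG concentrations and the incorporation of plasma FFA into DG" differ between UBO and T2DM (ANOVA), and adds a relation to insulin signaling. For ceramide, "we will use a similar statistical approach, except using intramyocellular ceramide concentrations and enrichments relative to plasma palmitate". The Study Summary compares niacin and saline days by paired t-test.

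**The concern.** The conclusion needs two things that the plan does not supply.

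The first is a lean reference. To say which lipid accounts for an impairment relative to lean people, one needs the size of that impairment and of the accompanying lipid excess. In this trial the control is saline in the same person.

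The second is a comparison between lipids. Calling a fall selective is a statement about DG versus ceramide. Two separate analyses do not test it: one lipid can reach significance and the other miss it when both fell by the same amount.

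At stake is the paper's mechanistic message. A report could name one lipid as the likely cause of insulin resistance when the data show only that one of two small-sample tests crossed a threshold.

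**Working it through.** **1. Is there a lean reference anywhere?** Apart from the sentence at issue, lean or normal-weight people appear as background (section 1.1), in the account of the cited acipimox study (section 1.2) and as the target for FFA titration (section 1.4). The schedule of events in section 6 has no lean cohort. The acipimox study is a poor substitute: by section 1.2's own account, its whole-muscle DG did not differ between lean, obese and T2DM at baseline. That section also faults it for measuring whole muscle only, whereas this trial looks at subcellular fractions.

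**2. Is there a DG-versus-ceramide test?** The named methods are paired t-test, linear regression, ANCOVA, ANOVA (UBO versus T2DM) and repeated measures ANOVA. The last mentions both lipids, for an expected lower tracer contribution during the clamp, but its factors are not stated. No lipid-by-treatment term appears, and *selective* has no threshold or definition.

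**3. The plan's own power figure.** Section 7.1 claims 90% power for a 10% improvement in insulin sensitivity with 5 subjects. Reading the ~5% reproducibility as the SD of the paired difference, the standardised effect is 10/5 = 2. The noncentral t (df 4, noncentrality 2√5 = 4.47, two-sided 0.05) gives 0.909, so the figure reproduces. It concerns glucose disposal. No SD or power is given for DG or ceramide, so the lipid calculation below has to use assumed ranges.

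**4. How often would equal effects look selective?** Assumptions: both lipids truly fall by the same standardised amount d (mean change divided by SD of the paired change); changes are normal with correlation ρ; each lipid has its own two-sided paired t-test at 0.05; *selective* means exactly one is significant. For ρ = 0 the probability is 2p(1−p), where p is the power of each test. At d = 0.7, for example, 2 × 0.506 × 0.494 = 0.500. For ρ > 0 it was simulated with 200,000 replicates per setting.

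| n = 10, d | power p | ρ = 0 | ρ = 0.5 | ρ = 0.8 |
|---|---|---|---|---|
| 0.5 | 0.295 | 0.415 | 0.301 | 0.194 |
| 0.7 | 0.506 | 0.500 | 0.353 | 0.225 |
| 0.8 | 0.616 | 0.475 | 0.336 | 0.212 |
| 1.0 | 0.802 | 0.316 | 0.237 | 0.153 |
| 1.2 | 0.921 | 0.146 | 0.118 | 0.079 |

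If the cohorts were pooled (n = 20), the figures would be 0.492, 0.337 and 0.211 at d = 0.5, and about 0.02 at d = 1.0.

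**5. What would a direct contrast do?** Take, for each person, log(niacin/saline) for DG minus log(niacin/saline) for ceramide, and test its mean against zero. The null is equal proportional change, and the error rate is 5% even when the two lipids have different SDs (0.050 to 0.051 in simulation with one SD twice the other). Dividing each change by its SD estimated from the same 10 people is not equivalent: under equal standardised effects that version rejects in 8% to 23% of studies over the same grid.

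**6. Power of the contrast.** For n = 10, 80% power needs a mean difference of 0.996, or about 1.0, SD of the contrast (1.16 for 90%). If each log change has SD 1 unit, the contrast has SD √(2(1−ρ)), so the detectable difference is 1.41, 1.00 or 0.63 units at ρ = 0, 0.5 or 0.8. For n = 20 pooled, 0.66 SD of the contrast gives 80% power.

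**The case against.** The best defence is that the sentence is interpretation, not a decision rule. It says a pattern will suggest what is most likely responsible. The primary objective, the primary endpoint and the hypothesis compare niacin with saline and do not require a choice between the lipids, and the Study Summary calls this a pilot. That stands: a reader might infer that the main conclusion depends on this step, and the documents do not support that.

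A reader might also take the remark about both lipids mattering in T2DM and only one in UBO as a planned test. It is offered as a possibility, by way of example.

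Nor does the plan say that *selective* means one significant and one non-significant result. That is a reading of an undefined word, and the repeated measures ANOVA could be built with lipid as a factor. The same biopsies and tracers supply both lipids, so zero correlation is a doubtful case to lead with. The planned interpretation also requires improved disposal and signaling and draws on regressions, none of which the simulation models.

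Finally, the lean phrase can be read as a premise, since section 1.1 treats impairment relative to normal-weight adults as already known. That explains the wording, but it does not supply the DG or ceramide excess needed to apportion the impairment between them. Tentative language does not fill either gap.

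**Conclusion.** The concern holds in a limited form. The stated conclusion goes beyond the design because there is no lean group, no named lean dataset and no specified DG-versus-ceramide comparison. Conditional on separate tests being used to judge selectivity, equally affected lipids would look selective in roughly 8% to 50% of cohort-level analyses. The range reflects assumed effects and correlations, because the documents give none for the lipids. It is not the rate of false mechanistic claims, and no single value in it should be quoted as such. The niacin-versus-saline comparisons themselves are untouched by this point.

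**What to change.** In section 7.2:

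- Delete the lean comparison, or name an external source and state its limits (including whole-muscle versus subcellular measurement). Confine the conclusion to the within-person niacin-versus-saline change.
- Name in advance the one DG measure and the one ceramide measure to be compared. Call a reduction selective only if the paired within-person contrast, log(niacin/saline) DG minus log(niacin/saline) ceramide, supports it.
- Report that contrast with a confidence interval and label it exploratory. Assess any UBO-versus-T2DM difference as a cohort interaction on the same contrast.

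This needs a wording change and one extra analysis of data already being collected, with no new participants, samples or visits. The cost is a narrower claim. At n = 10 the contrast will usually miss differences well below 1.0 SD of the contrast. The interaction is weaker still: with 10 versus 10 it needs about 1.32 SD for 80% power (two-sample noncentral t, df 18, noncentrality 1.32 × √5). An inconclusive interval should be reported as such, not as evidence that both lipids responded alike.

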rebound increase in FFA concentrations. Depending upon the degree of overnight suppression of FFA concentrations, the dose may be adjusted downwards or upwards (maximum rate of 2.8 mg/min) in subsequent studies. At 0400 h an infusion of [$U\text{-}^{13}\text{C}$]palmitate (330 nmol/min) will be initiated to trace FFA contribution to intramyocellular lipids in the euinsulinemic state (13,15). At 0600 h an infusion of [$6\text{-}^2\text{H}_2$]glucose will be started to trace glucose metabolism and continued till the end of the study. Resting energy expenditure will be measured by indirect calorimetry to permit interpretation of FFA flux data. A series of blood samples will be collected between 0830 and 0900 h to measure steady state plasma palmitate and glucose enrichment and concentrations. The volunteers will then undergo a vastus lateralis muscle biopsy as well as abdominal subcutaneous adipose biopsy together for measurement fatty acid metabolites and to provide material for the “pre-clamp” measures of insulin signaling; the niacin infusion will then be discontinued.

Beginning at 0915 h the volunteers will receive a primed, constant infusion of insulin (1 mU/kg/min) together with an infusion of 50% dextrose labeled with [$6\text{-}^2\text{H}_2$]glucose in order to maintain euglycemia. At the start of the insulin clamp the [$U\text{-}^{13}\text{C}$]palmitate will be stopped and [$^2\text{H}_9$]palmitate (400 nmol/min) will be started to measure the contribution of FFA to intramyocellular lipids during hyperinsulinemia (35). At the end of the 5 hour insulin clamp a second muscle biopsy will be collected from the contralateral leg from the first biopsy to avoid the effects of local trauma. This biopsy is taken at 5 h to allow us to measure the accumulation of [$^2\text{H}_9$]palmitate in the intramyocellular lipid metabolites listed above, as well as to detect the loss of [$U\text{-}^{13}\text{C}$]palmitate from the metabolites as a function of their turnover. A series of blood samples for glucose and palmitate enrichment will be collected just prior to each of these biopsies.

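### Section 7.2 infers the source of muscle DG and ceramides from enrichment ratios that, after about 5 h of tracer, do not separate source from pool turnover

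*Combined protocol and SAP*

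**What the plan says.** Under the primary hypothesis in section 7.2, the "ratio of DG palmitate:plasma palmitate" measures incorporation of plasma FFA into DG. Of DG enrichment relative to plasma palmitate, the section says: "This will provide us with as an index of de novo synthesis of DG from FFA".

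A preceding paragraph in 7.2 turns to source. It opens "A subtext to the DG and ceramide enrichment measures relative to plasma and palmitoyl-CoA is that" and continues "to the extent these molecules are synthesized from sources other than FFA, this will provide clues to alternate pathways that may be active". The next sentence is firmer: "We will be able to understand whether excess ceramides are due to" de novo synthesis or sphingomyelin hydrolysis, with a parallel statement for DG and phospholipid hydrolysis. The paragraph presents this ability as a strength of the study. It gives no estimator, cut-off or test for source, and section 7.2 contains no turnover term.

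Section 3.1 describes the tracers. [U-13C]palmitate starts at 0400 h and the first muscle biopsy follows blood sampling at 0830 to 0900 h. [2H9]palmitate replaces it at 0915 h, and the second biopsy, from the other leg, comes at the end of a 5 h clamp. The second biopsy is also meant to detect the loss of [U-13C]"palmitate from the metabolites as a function of their turnover".

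**The concern.** Product enrichment can lie below precursor enrichment for two reasons. Some new molecules may be made from something other than labelled FFA, or unlabelled molecules made before the tracer started may still be in the pool. One enrichment ratio cannot say which. Using palmitoyl-CoA as the precursor does not help, because the difficulty lies in the product pool.

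At stake is the mechanistic conclusion. If niacin slowed DG or ceramide turnover, or if turnover differed between the upper body obese (UBO) and type 2 diabetic (T2DM) groups, the ratio would change with no change of source. Following 7.2 as written, that could be reported as a shift in pathway.

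**Working it through.** The plan states no expected ratio, half-life or threshold, so there is no figure of its own to reproduce.

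**Inputs from section 3.1.**
- [U-13C]: "At 0400 h an infusion of" this tracer, and "A series of blood samples will be collected between 0830 and 0900 h to measure steady state plasma palmitate and glucose enrichment and concentrations", just before biopsy 1. Exposure is 0900 − 0400 = 5 h (at most 5.25 h, if the biopsy ran to 0915 h).
- [2H9]: 0915 h plus a 5 h clamp, so 5 h, ending at 1415 h.

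**Assumptions.** One well-mixed pool at steady state, constant precursor enrichment, and a half-life *h* shown as a range because the documents give none.

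**Step 1: the raw ratio.** With *f* the share of synthesis from FFA and *k* = ln 2 / *h*:

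R = f × (1 − exp(−5k)) = f × (1 − 2^(−5/h))

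With f = 1:

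| Half-life (h) | 1 | 2 | 5 | 12 | 24 |
|---|---|---|---|---|---|
| R | 0.97 | 0.82 | 0.50 | 0.25 | 0.13 |

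R reaches 0.95 only if the half-life is about 1.2 h or less.

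**Step 2: one ratio, many sources.** Take R = 0.50, so f = 0.50 / (1 − 2^(−5/h)):
- h = 5 h: 0.50 / 0.500 = 1.00
- h = 3 h: 0.50 / 0.685 = 0.73
- h = 2 h: 0.50 / 0.823 = 0.61
- h = 1 h: 0.50 / 0.969 = 0.52

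**Step 3: a change in turnover alone.** With f = 1, lengthening the half-life from 5 to 8 h lowers R from 0.50 to 0.35, a relative fall of 30%. Going from 2.5 to 5 h lowers it from 0.75 to 0.50.

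**Step 4: what the second tracer adds.** During the clamp the [U-13C] label is diluted by new molecules. With no label re-entry, the replaced fraction is

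P = 1 − E13(biopsy 2) / E13(biopsy 1)

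and f = R / P for [2H9] over the same 5 h. At half-lives of 2.5, 5 and 10 h, P = 0.75, 0.50 and 0.293.
- True f = 1: R = 0.75, 0.50, 0.293, and R / P = 1.00 each time.
- True f = 0.5: R = 0.375, 0.25, 0.146, and R / P = 0.50 each time.

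**Step 5: limits of that correction.**
- *Re-entry.* Suppose the 13C precursor stays at 5%, 10% or 20% of its earlier level during the clamp. At h = 5 h and true f = 1, E13(biopsy 2) / E13(biopsy 1) = 0.55, 0.60 or 0.70, so P = 0.45, 0.40 or 0.30 and estimated f = 0.50 / P = 1.11, 1.25 or 1.67. The bias is upward.
- *Noise.* In simulation (15% CV on each measurement, n = 20, true f = 1, lower 2.5% tail), P was zero or negative in about 9% of subjects at a 12 h half-life and 25% at 24 h. Dividing R by P within each subject gave about 16% false non-FFA conclusions at 24 h. Testing the paired difference R − P kept them at about 1 to 2%.

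**The case against.** The strongest reply is that the plan contains no rule to break. A reader might infer that any ratio below 1 will be declared a non-FFA source, and so that the declaration would be made almost whatever the truth. The documents do not support that reading. The paragraph calls itself a subtext, speaks of clues, and gives no cut-off or test. Nor would such a test always mislead: with an assumed 20% CV, n = 10 and f = 1, a two-sided 5% t-test of R < 1 would flag about 7% of the time at a 1 h half-life, 34% at 1.5 h and 86% at 2 h. The documents neither give nor exclude any of these half-lives, and the test is hypothetical.

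The investigators also clearly had turnover in mind, since section 3.1 designs the second biopsy partly to measure it. The reference to excess ceramides and elevated DG could mean comparing groups or days, with no benchmark of 1.

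These replies narrow the point but do not remove it. The sentence after the clues makes a firm claim to distinguish sources. The only bases named are enrichment ratios and concentrations, and 7.2 never says that the [U-13C] loss will enter the inference. A comparison between groups or days has the same ambiguity, as step 3 shows.

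A second tempting reading is that the main niacin–saline result is compromised. It is not. The primary endpoint in section 3.4 is the contribution of plasma palmitate to muscle lipids, compared by paired t-test in the Study Summary. That comparison does not use source attribution; only its interpretation as source, as opposed to turnover, meets the same limit. Glucose disposal and Akt phosphorylation do not depend on it either.

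**Conclusion.** The concern holds in a limited form: the source attribution promised in 7.2 is not identified by the quantities that 7.2 names. With about 5 h of each tracer, the same ratio of 0.50 fits an FFA share anywhere from 1.00 (5 h half-life) to 0.52 (1 h). For pools with half-lives under about 1 h the problem is negligible, since the ratio is then within about 3% of its ceiling; for slower pools it is large. The sizes rest on a one-pool model and assumed half-lives. The non-identification does not rest on any particular half-life: one ratio cannot fix two unknowns.

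This affects a mechanistic interpretation in a pilot study and leaves the primary comparison intact. It is worth correcting because the plan presents the interpretation as a strength and the data for a better one are already to be collected.

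**What to change.** Amend section 7.2 as follows.

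1. For the clamp period, base any source statement on the [2H9] product/palmitoyl-CoA ratio compared with the fraction of the pool replaced, estimated from the [U-13C] loss between the two biopsies and the measured pool size.
2. Make the comparison as a paired difference, or as a ratio of group means, with a confidence interval. Do not divide within subjects, which is unstable for slow pools. The ratio of means also becomes imprecise when little of the pool is replaced, so the difference is the safer default. Compare niacin with saline on the same quantity.
3. State that label re-entry makes the replaced fraction a lower bound, so that the corrected FFA share is biased upward and a real non-FFA source can be missed. State also that the two biopsies come from opposite legs, so differences between legs enter the estimate.
4. Label source attribution exploratory.
5. Withdraw the claim to separate de novo synthesis from hydrolysis for the basal [U-13C] period, which has no matching turnover estimate.

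The cost is revised wording and one further calculation per lipid and study day, with no new samples or procedures. The corrected quantity will be noisier than the raw ratio, and the mechanistic claim narrower.
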